## 11.4 Interim Analyses

As part of the interim monitoring there will be a single formal interim analysis of the efficacy data. This interim analysis will be on a comparison of the number of cases of severe COVID-19 (primary outcome (2)) between the BGG group and the control group for those recruited post the introduction of the placebo (second stage of the study). The timing of the interim analysis will be event driven, and will be conducted using a time-to-event analysis, censoring participants who have not had the event at the time of their last follow-up. This data will be used to provide Kaplan-Meier estimates of the survival curve in the BCG and control groups, which will be used to estimate the proportion with severe COVID-19 at 6 months. These proportions will be used to compare the two groups.

The timing of the interim analysis will be determined by the original sample size calculation. Under the original sample size calculation, with 1668 per group and an incidence of 4% in severe COVID-19 at 6 months in the control group and 2% in the intervention group, this would equate to 67 + 33 = 100 cases in total. We therefore planned to conduct a formal interim analysis of severe COVID-19 once there had been 100 cases of severe COVID-19.

The stopping rule to be used in the interim analysis will be based on an alpha spending function, where the threshold to identify efficacy is based on the amount of data available at the time of the interim analysis relative to the data available at the end of the trial. The threshold for the interim analysis and the remaining alpha for the final analysis if the study is not stopped at the interim will be calculated using the Group Sequential Test (GST) of Two Proportions in NQuery (PTT12-1) with an alpha-spending function based on the Pocock stopping rule. This calculation will be based on an overall alpha of 0.045 for the primary

outcome (2), and the amount of available information at the time of the interim analysis (calculated as the percentage of participants with outcome data on severe COVID by 6 months relative to the final sample size).

This interim analysis of severe COVID-19 will be performed on all of the participants randomised into Stage 2 of the trial up to the interim analysis time point, comparing all the participants who are randomised to BCG and those randomised to placebo.

A statistical analysis plan for the interim analysis will be written, shared with the DSMB and made publicly available prior to undertaking the interim analysis. This analysis plan will provide all the details of the interim analysis, including the threshold to be adopted for the interim analysis.

Given the dynamic nature of research in this field, the DSMB will be advised that this rule be used as a guideline rather than a formal rule, and should be interpreted in the context of external information and information on the efficacy of BCG vaccination on the incidence of symptomatic COVID-19.

#### 12 ETHICS AND DISSEMINATION

## 12.1 Research Ethics Approval & Local Governance Authorisation

This protocol and the informed consent document and any subsequent amendments will be reviewed and approved by the applicable human research ethics committee (HREC) prior to commencing the research at each site. A letter of protocol approval by HREC will be obtained prior to the commencement of the trial, as well as approval for other trial documents requiring HREC review.

#### 12.2 Amendments to the protocol

This trial will be conducted in compliance with the current version of the protocol. Any change to the protocol document or Informed Consent Form that affects the scientific intent, trial design, participant safety, or may affect a participants willingness to continue participation in the trial is considered an amendment, and therefore will be written and filed as an amendment to this protocol and/or informed consent form. All such amendments will be submitted to the HREC, for approval prior to being implemented.

#### 12.3 Protocol Deviations and Serious Breaches

All protocol deviations will be recorded in the participant record (source document) and on the CRF and must be reported to the CPI or delegate, who will assess for seriousness.

Those deviations deemed to affect to a significant degree rights of a trial participant or the reliability and robustness of the data generated in the clinical trial will be reported as serious breaches. Reporting will be done in a timely manner (the CPI or delegate to review and submit to the approving HRECs within 7 days, or as required).

Where non-compliance significantly affects human participant protection or reliability of results, a root cause analysis will be undertaken and a corrective and preventative action plan prepared.

Where protocol deviations or serious breaches identify protocol-related issues, the protocol will be reviewed and, where indicated, amended.

#### 13 CONFIDENTIALITY

Participant confidentiality is strictly held in trust by the participating investigators, research staff, and the sponsoring institution and their agents. This confidentiality is extended to cover testing of biological samples in addition to the clinical information relating to participating participants.

The trial data and all other information generated will be held in strict confidence. No information concerning the trial or the data will be released to any unauthorised third party, without prior written approval of the sponsoring institution. Authorised representatives of the sponsoring institution may inspect all documents and records required to be maintained by the Investigator. The clinical trial sites will permit access to such records.

All laboratory specimens, evaluation forms, reports and other records that leave the site will be identified only by the Participant Identification Number (SID) to maintain participant confidentiality.

Clinical information will not be released without written permission of the participant, except as necessary for monitoring by HREC or regulatory agencies.

#### 14 PARTICIPANT REIMBURSEMENT

In Australia and Europe, participants will not be reimbursed for their involvement.

As outlined in appendix 4 in Brazil in line with federal legislation, expenses resulting from participation in the study, such as transportation to the place where the vaccination will be carried out will be reimbursed. The amount will not be considered substantial and reimbursement system will be designed to reduce risk of reimbursement being considered compensation or inducement to participant in the trial.

## 15 FINANCIAL DISCLOSURE AND CONFLICTS OF INTEREST

This is an investigator-initiated study, and the funders will have no role in the study design, data collection and analysis, decision to publish, or preparation of the manuscript. MCRI holds no commercial interest in the manufacture and trade of BCG.

## 16 DISSEMINATION AND TRANSLATION PLAN

The results of the trial will be reported to the participants after analysis is complete. The results of this trial will be submitted to peer reviewed journals, presented at conferences and may form part of student theses.

The Chief Principal Investigator holds primary responsibility for publication of the results of the trial.

## 17.1 Appendix 1: Specimens for biobanking - completed biobank registration form

Document version & date	Version 1.1 24th Aug 2020
Name of the bank	BCG vaccine to prevent severe COVID-19 in healthcare workers (BRACE)
Custodian of the bank	Name: [name]
Purpose of the bank	To store data and samples collected in the ':BCG vaccination to Reduce the impact of COVID-19 in healthcare workers (BRACE)' trial so they can be used in future research related to infectious diseases and immunity.
Sample/data type(s) and	Data will be collected from
where these will be accessed from and over what time period	Questionnaires and test results obtained as part of the research project 'BCG vaccination to Reduce the impact of COVID-19 in healthcare workers (BRACE)', by members of the research team.
	Blood and/or swab samples will be obtained via this research project and stored for an indefinite period of time.
	The samples/data may be sent overseas for future research related to infectious diseases, immunology, or vaccines.
	Data stored includes:
	- Demographics (e.g. age, gender, date)
	- Environment (e.g. household members, exposure to SARS-CoV-2 positive people, role in the hospital, TB exposure, previous vaccinations)
	- Study outcome related data (e.g. SARS-CoV-2 test results, BCG and influenza vaccine reactions, illnesses during study period, data generated from the laboratory analysis of samples collected)
	Sample types stored:
	- Swabs
	- Plasma
	- Serum
	- Peripheral blood samples
	- Granulocytes and whole blood
	- Nucleic acid
	After data ceases to be collected directly from participants, data may be obtained/generated via access to their medical records, government data sets or as samples are analysed and the data are added back into the data/biobank.

## Sample/data identifiability

Clinical data in 'BCG vaccination to Reduce the impact of COVID-19 in healthcare workers (BRACE)' will be collected and stored in a REDCap database; a secure password-encrypted online database, or similar electronic database hosted by MCRI.

Data will be stored in re-identifiable format with the key held by the custodian or delegate. The REDCap database or comparable database will be hosted on the secure Murdoch Children's Research Institute (MCRI) server and backed up regularly by MCRI Information Technology.

Only members of the research team involved in data collection or data management will have access to the project's REDCap database or similar electronic database.

Samples will be stored (frozen) in re-identifiable format by using study ID number or tube barcodes.

All data associated with sample storage location and tracking will be stored in a separate REDCap database or similar electronic database. Access to this database is limited to members of the research team working in data/sample management or sample processing.

Laboratory generated data, any data collected outside of REDCap and data exported from REDCap or similar electronic database, will be stored in re-identifiable format by study ID. The data will be stored on the MCRI server in restricted folders on the Infectious Diseases group drive, as per MCRI policy.

Samples/data stored in re-identifiable format can be linked by the custodian or delegate to participants' identifiable information if it is ethically appropriate and required.

# Criteria for Bank participants

Consenting to the project includes allowing the participants' data and samples to be used as defined in the protocol.

In addition there is an optional consent in the PICF for the storage of participants' biospecimens and participants' reidentifiable data for use in future research related to infectious diseases and immunity.

Inclusion criteria for Bank participants

- Recruited participant in the research project 'BCG vaccination to Reduce the impact of COVID-19 in healthcare workers (BRACE))'
- Provided informed consent for their data and samples to be stored for future ethically approved research (extended consent) related to infectious diseases and immunity.

Access process for	Researchers must discuss their research plan with a member of				
obtaining the samples/data	the research team of the project 'BCG vaccination to Reduce the impact of COVID-19 in healthcare workers: (BRACE))'. The following will be taking into consideration:				
	- Scientifically justifiable hypothesis and aims				
	- Study design is appropriate to achieve study aims				
	- Inclusion/exclusion criteria for participants appropriate to answer question				
	
 
If the research proposal is deemed to have merit, the researcher will complete a REDCap (or similar electronic database) access form detailing the proposed design, participants, data +/- samples that they would like access to.
 
				
	This will be reviewed by the custodian (or delegate) of the data who will need to take into account the following, before approval is granted:				
	
 
Does the research plan involve research in the area of immunology or infectious diseases? If not, it is outside the scope of the data/biobank. To use the data one of the following will be required:
 
				
	o a new project approved by the RCH HREC and participants contacted for their consent				
	o a new project approved by the RCH HREC and a waiver of consent granted				
	- Is the planned analysis feasible with the data/samples available in the data/biobank?				
	
 
Are there competing interests for the sample/data type in question?
 
				
	
 
Is another researcher already analysing the data in a similar way and would collaboration on the existing project be more appropriate?
 
				
	The access form for access to the data/biobank will be kept on the REDCap database or similar electronic database.				
Sample and data input	Members of the research team working in data/sample management will input the data and samples to the data/biobank.				
Location of the Bank	Samples will be stored in the MCRI freezer farm or in the Infectious Disease Group's freezers, and may be distributed to other collaborating laboratories where they may also be stored.				

Confidentiality/security of samples/data	Data will be stored in a REDCap online database or similar electronic database, hosted on the secure Murdoch Children's Research Institute (MCRI) server, as well as in restricted electronic folders on the MCRI Infection and Immunity group drive.  Members of the research team of the project 'BCG vaccination to Reduce the impact of COVID-19 in healthcare workers (BRACE)' involved in data/sample collection or management will have open access to the bank data/samples.
	No identifying data will be provided to researchers using data/samples from the biobank. To re-identify data/samples, the custodian (or delegate) will have access to the key, but will not pass this information onto researchers unless approved by ethics, or as required by law.
	Data stored on REDCap database or similar electronic database will be password protected, and hosted on the secure MCRI server. This is backed up regularly by MCRI Information Technology.
	The Bank will be secure against unauthorised access and passwords will be changed at regular intervals (as per MCRI policy).
	The custodian (or delegate) will ensure removal of access to data once a project is finished or a researcher leaves the project.
Destruction of samples/data	Destruction of samples/data will occur upon participant request. This will be managed by the custodian (or delegate).
Modifications to Bank Protocol	If a change of purpose/data type/type of samples is to be considered, the custodian (or delegate) is required to submit to the HREC for approval and either contact the participants to obtain consent, or a waiver must have been granted.

Confidential

17.2 Appendix 2. Collection of stool samples from a subset of BRACE participants

Background and Rationale:

For reasons that are poorly understood, B and T cell responses to vaccination (including BCG

vaccination) are highly variable between individuals and between different populations. While

many host factors, such as genetics, can influence inter-individual variation in these responses,

increasing evidence shows that the gut microbiota, a large and diverse group of

microorganisms that colonise gastrointestinal tract (GIT), plays a key role in shaping immune

responses to vaccination (reviewed Lynn & Pulendran, 2017). For instance, in human infants,

the relative abundance of several bacterial species in the stool microbiota has been associated

with vaccine-specific IgG and T cell proliferation responses (Huda et al., 2014). Similarly, the

composition of the stool microbiota in infants from rural Ghana was correlated with responses

to the oral rotavirus vaccine (Harris et al., 2017). Interestingly, germ-free mice have also been

found to have impaired antibody responses to immunization with the model antigen

ovalbumin (Lamousé-Smith et al., 2011) and to the non-adjuvanted influenza vaccine (Oh et

al., 2014). Moreover, one of the principal investigators involved in this trial has recently found

that, in mice, dysregulation of the microbiota leads to significantly impaired B and T cells

responses to five different adjuvanted and live vaccines (including BCG) that are routinely

administered to infants worldwide (Lynn et al., 2018). Restoring the commensal microbiota

rescued impaired responses (Lynn et al., 2018). These data strongly suggest that the

composition of the gut microbiota plays an important role in specific immune responses to

vaccination. Whether the gut microbiota also influences non-specific effects of vaccines is

currently unknown.

Primary objective of exploratory sub-study:

In a subset of BRACE trial participants consenting for an optional stool sample collection at

baseline, determine whether the composition or metagenome-encoded function of the stool

microbiota is correlated with either specific or non-specific immune responses to the BCG

vaccine.

## Secondary objectives of exploratory sub-study:

- Assess whether the composition of the stool microbiota is associated with any of the other primary, secondary, or exploratory outcomes described in the study protocol.
- Characterise the composition of the stool microbiota in participants in the trial and investigate whether the composition of the microbiota is altered at 3 or 12 months later.
- Assess whether immunisation with BCG leads to an altered microbiota at 3 or 12 months compared to participants receiving the placebo.

#### Outcomes:

Microbiota composition, including identities and the relative abundance of the bacteria present and their encoded microbial genes.

## Population:

BRACE trial participants consenting for an optional stool sample collection at baseline, 3 months and 12 months.

## **Study Duration:**

As per the BRACE trial protocol – 2 years.

## Participant Duration:

12 months from randomisation.

#### **Sub-study Locations:**

Optional inclusion for Australian sites.

## Potential risks and benefits:

#### Known potential risks:

This sub-study involves minimal risk to participants. Appropriate collection containers will be provided to participants to facilitate stool sample collection, storage and transport. A small stool sample will be collected by the participants at home. The tube contains a reagent that stabilises DNA at room temperature for up to 14 days. Participants will return the sample via a pre-paid addressed envelope. There will be no financial cost to the participant.

## Known potential benefits:

This sub-study is exploratory in nature and is not expected to provide any direct additional benefit to the participants. The findings of the study, however, may be of significant value for understanding the role of the microbiota in influencing responses to vaccination.

#### Sub-study design:

#### Consent:

An additional option has been added to the BRACE online consent form to allow participants to optionally consent for a stool sample collection at baseline, 3 months and 12 months. The BRACE participant information and consent form (PICF) has been also modified to explain to participants the process for collecting stool samples and why they are being collected. If a participant declines to consent for stool sample collection this will not affect their participation in the BRACE trial (assuming all other inclusion and exclusion criteria are met). Sample collection process:

Participants consenting for a stool sample collection will be provided with a collection pack at existing study visits at baseline, 3 months, and 12 months. The provided pack will contain: Instruction sheet, gloves, pathology stool pot, stool specimen collector tube and spoon set, protective plastic carrying tube, specimen bag, labels for identification of samples and prepaid addressed envelope (for return postage). Participants will take the collection pack home with them and follow the following instructions to collect and return the stool sample.

#### Collection instructions:

- 1. Wash hands thorough and apply gloves.
- 2. Collect stool sample into the pathology stool pot within 1-3 days of study appointment.
  - Note: Method of collecting the stool sample must prevent stool from falling into toilet water to avoid sample contamination.
- 3. Unscrew the stool specimen collector tube cap and use the spoon to scoop two spoonsful of stool (approximately 2 gram or 2mL in volume) from the sample.
- 4. Place the sample in the stool specimen collector tube.
- 5. Tighten the cap and shake to mix the contents thoroughly (invert 10 times) to create a suspension. Note: Some stool material may be difficult to re-suspend. As long as the material is suspended, the sample is stabilized. Foaming/ frothing during shaking is normal.
- 6. Dispose of gloves, unused stool material and the pathology stool pot and wash hands thoroughly.
- 7. Place stool specimen collector tube into the protective plastic carrying tube.

- 8. Place carrying tube into specimen carrier bag.
- 9. Place the sealed specimen bag containing the sample into the provided postage-paid reply envelop and post within 7 days of sample collection.
- 10. Samples will be returned to the nearest BRACE site laboratory for storage at -80C.

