## 4.7 Pre-randomisation blood sample

To remain eligible for randomisation in BRACE a pre-randomisation blood sample must be provided. This blood sample will be taken at enrolment but can be taken up to 24 hours prior to randomisation. This sample cannot be taken after administration of the intervention or placebo.

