## 6 RANDOMISATION AND BLINDING

Once consent has been obtained, and following baseline assessment, eligible participants will be recruited and randomised on the day of the enrolment via REDCap. Randomisation will be to intervention or placebo group with an allocation ratio of 1:1, using a web-based randomisation procedure. The randomisation schedule and web-based service will be provided by an independent statistician from the Clinical Epidemiology and Biostatistics Unit (CEBU) at the Murdoch Children's Research Institute. Randomisation will be in randomly permuted blocks of variable length (2, 4, or 6). Randomisation will be stratified by stage of the study (prior to or post the addition of the placebo vaccination), study site, by age (<40 years; 40 to 59 years; >=60 years) and by presence of comorbidity (any of diabetes, chronic respiratory disease, cardiac condition, hypertension). Stratification by age is necessary for data analysis because

[figure not shown]
older ages are associated with a greater likelihood of developing severe COVID-19. Likewise, presence of comorbidity is associated with a greater risk of developing severe COVID-19. Each study site will have their own randomisation list stratified by study stage (where relevant), age and presence of comorbidity.

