# Sub-set of participants

#### 7.3 Description of procedures

The procedures related to recruitment, consent, eligibility confirmation, randomisation and intervention are described in sections 4 and 5 of this protocol. The procedure for blood collection is described in the relevant SOP. Capture of applicable adverse events is described in section 8.

In Brazil only, a baseline respiratory swab will be collected as outlined in appendix 4.

After randomisation there are two key aspects of the 1-year follow-up period; questionnaires and sample collections for SARS-CoV-2 identification (respiratory swabs or blood samples). Participants will be asked to complete a questionnaire using the smartphone application (app) designed for the trial, electronic messages or via phone calls to report symptoms, access SARS-CoV-2 testing through the public health system and if needed self-collect a respiratory swab each time they have a febrile illness or a respiratory symptom. Where app is utilised, participants will be trained on how to use the app on day of enrolment.

st In indicated Infectious Diseases clinician, or state-based organisation, as appropriate

\*\* Optional consent for additional biological sample including blood sample when illness reported

\*\*\* Brazil only as outlined in Appendix 4

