#### **Blood samples**

- At randomisation, a blood sample will be taken for later assessment of seroconversion (production of specific anti-SARS-CoV-2 antibodies). This will identify participants who had SARS-CoV-2 exposure and immunity prior to commencement of the study.
  - The baseline blood samples will be analysed in batch months after randomisation, so there will be no clinically actionable results. We will provide individualised results to participants via email after completion of the trial.
     This email will be sent to the applicable HRECs to review before being sent out to any participant.
  - o In Brazil, IGRA testing will be completed on pre-randomisation and 12-month blood samples as outlined in appendix 4.
- At 3 months and 6 months (+ 42 days) post randomisation, the study team will
  coordinate to collect study blood samples from participants and in a subset of
  participants at 9 and 12 months (+ 42 days) post randomisation. This will identify

- participants who had an immune response to SARS-CoV-2 (surrogate marker of infection) during the study. This is needed to determine asymptomatic SARS-CoV-2 infections.
- Blood samples will also be taken for assessment of the immune system. This will be
  used to meet the planned exploratory analyses related to vaccine induced changes in
  the immune system. These blood samples will be taken at the same time as blood
  collection for serum or plasma samples (i.e. at randomisation and post
  randomisation)
- In the eventuality that it is unfeasible to collect swab samples to confirm SARS-CoV-2 infection at the time of febrile or respiratory illness episodes (or conduct a validated RAT test), seroconversion may be used to associate episodes of febrile or respiratory illness with SARS-CoV-2 infection. Therefore, for episodes of febrile or respiratory illness where a swab sample cannot be taken, 1 month after the onset of symptoms (expected peak post-infection antibody production), participants may be asked to come to the hospital to provide a blood sample. If rapid point-of care testing is available, these tests may be distributed to participants to self-test. Should these alternative methods of testing become required, an amendment will be submitted to HRECs to outline the process and submit any information for participants. This testing will not be conducted without further consultation with and approval from the HRECs, including providing the HRECs with details of the test and its efficacy.

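### In the stool sub-study, the sample labelled baseline is ordinarily collected one to three days after BCG or placebo has been injected

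*Protocol*

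**What the plan says.** Under the consent and sample collection text of Appendix 2 (section 17.2), participants who agree to stool collection "will be provided with a collection pack at existing study visits at baseline, 3 months, and 12 months". The next step is done at home: "Participants will take the collection pack home with them and follow the following instructions to collect and return the stool sample". The collection instructions then set the timing: "Collect stool sample into the pathology stool pot within 1-3 days of study appointment".

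Section 6 says that "eligible participants will be recruited and randomised on the day of the enrolment via REDCap". The schedule of assessments (section 7.2) places allocation, the BCG or saline injection and the baseline blood in one column, t0. The earlier column, t-1, holds only the eligibility screen, consent, contact details and the baseline questionnaire.

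For blood, section 4.7 gives an explicit order: "This blood sample will be taken at enrolment but can be taken up to 24 hours prior to randomisation", and "This sample cannot be taken after administration of the intervention or placebo". Appendix 2 has no matching rule for stool.

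At 12 months, section 7.3 limits study blood to a subset of "participants at 9 and 12 months (+ 42 days) post randomisation". The mark on the 9- and 12-month blood entries in the schedule is explained as "Sub-set of participants". The protocol does not define who is in it.

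**The concern.** A pack received at the visit and filled at home is filled after the visit, and the injection is given at the visit. The value called baseline is then a post-treatment value.

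Two uses of it are exposed. The sub-study's primary objective relates stool collected at baseline to specific and non-specific immune responses to BCG, and its rationale is that the microbiota shapes vaccine responses. That reading needs a measurement from before vaccination. One secondary objective asks whether composition has changed 3 or 12 months later, which needs a true starting value. If BCG alters the microbiota in the first days, a correlation in the BCG arm could partly reflect the vaccine's effect, and the measured change would start from a shifted point.

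There is also a delivery question at 12 months. Appendix 2 relies on an existing visit, yet the main schedule gives an in-person procedure then only to an undefined subset.

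**Working it through.** No sample size, power or alpha figure is involved. The check is a day count and a comparison of sections.

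**Timing of the baseline sample.** Let the injection be day 0. Collection day = day the pack is received + days from appointment to collection.

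| Route | Pack received | Interval applied | Collection day |
|---|---|---|---|
| Usual flow (section 6; schedule column t0) | 0 | 1 to 3 days | 0 + 1 = +1 to 0 + 3 = +3 |
| Pack issued at a blood draw 24 h before randomisation (section 4.7) | -1 | 1 to 3 days | -1 + 1 = 0 to -1 + 3 = +2 |
| Same early draw, interval read as up to 3 days | -1 | 0 to 3 days | -1 + 0 = -1 to -1 + 3 = +2 |

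In the usual flow every sample follows the injection. A pre-injection sample is possible only on the early-draw route, and only at its earliest edge. Appendix 2 does not say that packs are issued at such a draw.

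**Which objectives use the sample.**
- Primary objective (correlation with immune response to BCG): uses the baseline sample directly.
- Change in composition by 3 or 12 months: uses it as the reference.
- BCG versus placebo at 3 or 12 months: a comparison of randomised groups that does not need it.

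**The 12-month visit.** The 12-month column of the schedule lists the weekly survey, the 12-month survey, swab instructions if indicated, and blood in the subset. Blood is the only entry that implies attendance. Brazil's 12-month draw (Appendix 4) does not help, because the stool sub-study is offered at Australian sites. Section 7.3 allows a self-collected dried blood spot and section 7.5.1 lets participants decline further blood, so membership of the subset does not guarantee a visit either.

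**Can collection still be changed?** Section 1.3 expected recruitment to end in March 2021. If the last participant was randomised on 31 March 2021, the 12-month point is 31 March 2022. Adding the 42-day window gives 12 May 2022, and 3 more days for stool gives 15 May 2022. This protocol version is dated 17 May 2022. On the expected timetable, collection was already over.

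**The case against.** The instruction says of the appointment, not after it, and section 4.7 allows contact up to 24 hours before randomisation. A reader might infer that every baseline stool sample is post-injection. The text supports only nearly every, because of that route.

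The objectives speak of correlation and claim no cause, and no section shows that one intradermal dose alters gut microbiota within three days. This stands as a limit on size. The protocol does not treat the first days as immunologically silent, however. Section 2.2 describes protection in children within days of vaccination, and section 2.3.1 describes local reactions to revaccination beginning at 24 to 48 hours. Neither is evidence of a gut effect, but together they mean that its absence should be checked rather than assumed.

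A reader might also infer that the 3- and 12-month arm comparison is compromised by adjusting for a post-treatment value. The documents do not support this: no section plans such an adjustment, and the comparison stays randomised.

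A further tempting inference is that some stool participants have no 12-month visit. The blood subset is undefined and could contain all of them, so this is a gap to clarify and not a demonstrated loss. Nothing suggests that the subset differs by arm.

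Finally, on the expected timetable new delivery rules come too late. That largely stands, and it moves the weight of the remedy to labelling and analysis.

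**Conclusion.** The point holds, as a minor one. Followed as written, Appendix 2 yields a sample labelled baseline that ordinarily lies 1 to 3 days after injection, while the same protocol bars this for baseline blood. It weakens two things: reading the primary sub-study objective as pre-vaccination microbiota relating to BCG response, and describing change from baseline at 3 and 12 months. It does not touch the randomised stool comparison at those times or any primary outcome of the trial.

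The conclusion assumes that packs were issued at the visit where the injection was given, as Appendix 2, section 6 and the schedule together imply. The size of any resulting distortion cannot be derived from the protocol. The 12-month pack is a secondary point of clarification.

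**What to change.** **Any collection still to come.** Supply the pack before the visit, and require the sample to be taken before the injection with date and time recorded. Online consent and contact details already precede t0, so the cost is outbound postage and a wording change. Some late bookers would have no baseline sample.

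**Samples already collected.**
- Label them by day since injection instead of as baseline.
- Compare them between arms, with an estimate and interval, before using them as pre-vaccination predictors. A non-significant difference in a small subset would not establish that there is no effect.
- Alternatively, describe change from a true baseline in the placebo arm only, where the injection is saline.
- Do not enter them as a pre-treatment covariate in the 3- and 12-month comparisons.

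This costs a derived variable and one extra table.

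**The 12-month pack.** Reconcile Appendix 2 with sections 7.2 and 7.3 by stating either that stool participants belong to the 12-month blood subset or that their packs are posted. If collection is complete, record which of these was done. This needs one sentence.
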